4.7 Diagnosis of Cancer

If a participant in the control or experimental group is diagnosed with cancer over the course of the study, the study team may collect blood samples at different timepoints before, during and after their cancer treatment. This blood collection is optional. These samples may be sequenced by the study team to better understand the performance of the cfDNA blood test. If a participant in the experimental group develops cancer, optional

research blood samples collected after the diagnosis may not be analyzed immediately by the study team, and results will not be returned to the participants. Any samples not used by the study team will be banked with the CHARM Biobank for use in future research (for example, to understand how a cfDNA blood test could be used to monitor response to treatment).

If a participant is diagnosed with cancer over the course of the study, patient-outcome questionnaires will no longer be collected alongside the optional blood collections.

4.8 Collection of Clinical Data

Clinical data will be collected from participants' medical record and the medical history and demographic questionnaires completed by participants following informed consent (please see "Demographics and Medical History Questionnaire"). Participants will be given the option to complete the questionnaire in person (e.g., if the consent process occurred in person), or electronically. If completed electronically, the questionnaire may be emailed to the participant, or the participant may complete the questionnaire via REDCap (a link will be emailed to them). If a patient is not able to complete the questionnaire electronically, a physical copy may be mailed to them with a return envelope. The questionnaires will record the patient's study ID only (name, DOB, MRN will not be recorded). Updates to questionnaire results may be collected by the study team over the course of the study.

If a participant receives care at more than one study site, their medical records from any of the other sites may also be looked at, regardless of which site they are enrolled at for this study. Sharing of any study records between sites for patients who have received care at multiple sites will only occur following execution of appropriate DTAs. Study team members may also request medical history information from participants directly, if not available in their medical records (e.g. by setting up a phone call). Additionally, study team members may ask a participant to complete a Release of Information (ROI) form (appended to this application), to request medical records from external hospitals/clinics.

The following clinical data will be captured over the course of this study for all participants:

- Demographic information (including date of birth, self-reported gender and sex assigned at birth, ethnicity).
- Genetic diagnosis and date.
- Past medical history, including but not limited to personal history of cancer, cancer risk factors, cancer screening history, pregnancy status, current medications, comorbidities.
- Cancer screening – results and dates of any cancer screening/diagnosis investigations done prior to, or during the study (including the diagnostic investigations done in follow-up to a positive cfDNA test result).

- For participants with a history of cancer or diagnosed with cancer during the study – pathology information, imaging and procedure results, treatment details.
- Family history of cancer.

Collection of the above clinical information, and subsequent comparison to the results of the cfDNA test, is necessary in establishing the sensitivity, specificity, and PPV and NPV of the cfDNA test. The above clinical information will be documented for all participants for up to 7 years from the date of study enrollment. Continued collection of clinical data after all sample collection for the purpose of the study has been completed will be necessary to establish function of cfDNA test (for example, clinical detection of cancer may occur after the 5-year period).

4.8 Participant Questionnaires and Interviews

4.8.1 Patient outcome questionnaires

All participants will be invited to complete patient-outcome questionnaires throughout the course of their participation in the study (appended to this application):

- At the time of study enrollment, before randomization into the control or experimental group, participants will be provided a patient-outcome questionnaire.
- Experimental group:
 - Participants in the experimental group will be asked to complete a patient-outcome questionnaire following each result disclosure by the study team (approximately 45 days following the blood collection).
- Control group:
 - Participants in the control group will be asked to complete the patient-outcome questionnaire up to 3 times a year.

The questionnaire will include validated measures focused on anxiety, cancer worry, disease uncertainty, empowerment, among other emotional outcomes. Questionnaires will be completed electronically via REDCap, and participants will be emailed a link to the questionnaire by the study team. If a participant is unable/not comfortable completing a questionnaire electronically, a paper copy may be mailed to them. Each questionnaire should take no longer than 20 minutes to complete. Questionnaires will record the participants Study ID. Questionnaires will be analyzed jointly with [name] at Unity Health. Demographic and health information (e.g. genetic diagnosis, cancer history) will be shared with [name] study team, to aid in the interpretation of the questionnaires. Appropriate DTAs will be established prior to the sharing of any data. Completion of the questionnaires will be encouraged by the study team, however will not be mandatory for continued study participation (i.e. if a participant does not complete a questionnaire, they will not be removed from the study).

As the questionnaire includes some questions that participants may find distressing, we will include an option at the end of the questionnaire for participants to indicate that they would like to speak with a member of the study team. Together with the study Patient Partners, the study team will put together a list of resources, that may be shared with participants if needed.

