4.5 Clinical Reporting

Blood test requisitions will be completed online through the OICR Genomics Requisition Portal by an authorized study team member. The following PHI will be recorded on the requisition form: participant name, date of birth, sex. The OICR requisition will also capture the participant's germline pathogenic variant in their respective HCS gene. The OICR Genomics Requisition Portal retains all PHI in an access-restricted database accessible only to requisitioners (i.e., study team members who will submit the requisition) and ACMG/CCMG licensed Geneticists who will sign out each report. The ACMG/CCMG licensed Geneticists will be part of the study team and will be internal to UHN. No OICR staff member will have access to the PHI submitted to the Requisition Portal.

We aim for the clinical report to be returned to the study investigator within 45 days of sample receipt by OICR, barring holidays and unforeseen circumstances. Clinical reports will be returned electronically, via OICR's online reporting system. Only the study investigator and designated team member will have access to the reporting system. The study team member will log into the OICR Genomics Requisition System and view/download a copy of the clinical report. The clinical report will contain PHI (patient name, DOB) and will be stored by the study team in a password-protected folder on a secure UHN network (UHN Sharepoint), only accessible by delegated study personnel. Per UHN Research Quality Integration's feedback, study clinical reports will be uploaded to EPIC.

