Power analysis is based on the primary outcome of improved cancer detection at various diagnosis rate scenarios of the study cohort at the end of the study, range with current 5% detection rate for all HCS without cfDNA modeling, up to 10% should cfDNA improve

detection. Based on the power analysis, our study with 1,000 patients will achieve >97% statistical power to detect at least 2% increased diagnosis rate attributable to cfDNA testing with 2-sided significance level at 0.05.

Lastly, analysis of the survey data will be led by [name] at Unity Health and [name] at Memorial University. DTAs will be established and signed by all institutions, prior to sharing of any data. Baseline adjusted mean differences between groups with 95% confidence intervals will be calculated for test-specific distress and uncertainty, generalized distress, anxiety, empowerment and quality of life; a regression framework for hypothesis-generating purposes will be used. Estimates of variance and correlation among emotional outcomes and empowerment, and quality of life and between groups will be determined. Proportion of cases and drop outs from rural/remote geographic regions across arms will be compared using a chi square test. P-values are set at 0.05 (two-tailed).

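### Patient-outcome questionnaires follow each result disclosure in the experimental arm but have no fixed time in controls, so the planned between-arm differences mix a short-term reaction to disclosure with any lasting effect of testing

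*Protocol*

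**What the plan says.** Protocol section 4.8.1 sets three questionnaire rules.

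- Baseline, both arms: "before randomization into the control or experimental group, participants will be provided a patient-outcome questionnaire".
- Experimental arm afterwards: "Participants in the experimental group will be asked to complete a patient-outcome questionnaire following each result disclosure by the study team".
- Control arm afterwards: "Participants in the control group will be asked to complete the patient-outcome questionnaire up to 3 times a year".

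Table 1 in section 4.12 shows three forms a year for four years, not split by arm. It does not tie the control forms to any date or event.

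Section 4.7 adds that, once a participant is diagnosed with cancer, "patient-outcome questionnaires will no longer be collected alongside the optional blood collections".

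Section 8.0 states the comparison: "Baseline adjusted mean differences between groups with 95% confidence intervals will be calculated for test-specific distress and uncertainty". The same sentence goes on to generalised distress, anxiety, empowerment and quality of life, and describes the regression as hypothesis-generating. Section 3.2 hypothesises that a cfDNA testing programme will lower distress, uncertainty and anxiety. Section 4.11 lists patient-reported outcomes as the fourth endpoint.

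**The concern.** Randomisation and baseline adjustment protect a comparison of means only if the follow-up measurements are taken in the same way in both arms. Here they are not. Every experimental form after baseline follows a disclosed result, while control forms fall at times the protocol does not define.

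Section 6.0 expects up to about 5-10% of experimental participants a year to receive a positive result. At least 90% in any year would therefore hear only negative results, and that arm is sampled mainly after news that no cancer signal was found. Any relief would tend to lower distress, uncertainty and anxiety, which is the direction hypothesised in section 3.2. The wait between a draw and its result has no scheduled form.

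A reader of the reported difference could not separate a passing response to disclosure from a lasting effect of being in a testing programme. A later analysis plan cannot recover time points that were never collected.

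A second, smaller issue is that questionnaires may end at cancer diagnosis, an outcome the test is meant to bring forward or make more frequent.

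**Working it through.** The protocol gives no SD, effect size, sample size or power for the questionnaires, so there is no figure to reproduce. The power statement in section 8.0 concerns cancer detection. The calculations below are in SD units and only show scale.

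**Inputs from the protocol**
- 500 participants per arm (Protocol Summary).
- Diagnosis scenarios: 5% without cfDNA testing, up to 10% with it; the smallest increase considered is 2 percentage points, giving 7% (section 8.0).
- Positive results: up to about 5-10% of experimental participants a year (section 6.0), so 1 - 0.10 = 0.90 or more have only negative results in a year.
- Two-sided 0.05 for the survey analysis (section 8.0).

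**Assumptions (not in the documents)**
- A net average shift of 0.1 to 0.3 SD on post-disclosure forms, relative to an average moment, with no lasting effect of testing. Net means after allowing for positive results, which would pull the other way.
- Diagnosed participants score 0.25 to 1.0 SD worse than others.
- Everyone not yet diagnosed answers at the time point compared.

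**Timing**

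Responders: 500 x 0.95 = 475 controls and 500 x 0.90 = 450 experimental.

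SE of the difference = sqrt(1/475 + 1/450) = 0.0658 SD. The 95% half-width is 1.96 x 0.0658 = 0.129 SD.

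The chance that a pure timing shift t is declared significant is approximately Φ(t/SE - 1.96).

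| Assumed shift t | t / SE | Chance of significance, no lasting effect |
|---|---|---|
| 0.1 SD | 1.52 | 0.33 |
| 0.2 SD | 3.04 | 0.86 |
| 0.3 SD | 4.56 | 0.995 |

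Missing forms would widen the SE. Adjustment for a correlated baseline would narrow it.

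**Stop at diagnosis, if it applies in both arms**

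Participants affected: 500 x 0.05 = 25 controls, against 500 x 0.07 = 35 to 500 x 0.10 = 50 experimental.

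Shift in the mean difference = (p_exp - p_ctrl) x d, where d is the gap for diagnosed participants.

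- 7% against 5%: 0.02 x 0.25 = 0.005 SD to 0.02 x 1.0 = 0.02 SD.
- 10% against 5%: 0.05 x 0.25 = 0.0125 SD to 0.05 x 1.0 = 0.05 SD.
- Equal diagnosis rates: 0.

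The largest value is 0.05 / 0.0658 = 0.76 SE. It also uses the end-of-study share diagnosed, so earlier time points would be affected less.

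**The case against.** The strongest reply is that repeated disclosure is part of the programme named in section 3.2, so a response to it is partly a genuine effect of testing. That is fair, and the shift should not all be called false. But forms taken only after disclosures describe one part of the cycle, and the planned contrast cannot say how much of a difference persists.

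The protocol also gives no interval between disclosure and form, so forms need not be completed at the moment of relief. This stands as a limit on size: the 0.1 to 0.3 SD range has no support in the documents.

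Visit windows and missing-form handling are often left to an analysis plan. That does not answer the point, because the protocol itself fixes when data are collected.

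The documents do not support several stronger readings that a reader might infer:

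- **Controls give fewer forms.** Table 1 schedules the same three a year for everyone.
- **All questionnaires stop at diagnosis.** The wording in section 4.7 may mean only that the optional post-diagnosis draws carry no form.
- **Only the experimental arm stops.** The sentence in section 4.7 covers a participant in either arm.
- **Test-specific distress has no baseline or control counterpart.** The questionnaire is listed as appended but is not shown, so its items cannot be checked.
- **The turnaround times conflict.** Section 4.8.1 gives "approximately 45 days following the blood collection". Section 4.5 aims for a report "within 45 days of sample receipt by OICR", and section 4.6 allows up to two weeks more, so 45 + 14 = 59 days. That sets an approximate time against the sum of two upper targets, and it has no bearing on bias between arms.

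**Conclusion.** The point holds for timing. The protocol prescribes different measurement rules for the two arms and then plans to compare their means. The likely direction favours the study's hypothesis if negative results bring short-term relief. The size is unknown: under the assumed shifts it ranges from about 1.5 to 4.6 SE, enough to produce a significant difference without any lasting effect.

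The possible stop at diagnosis is a minor addition. It depends on how section 4.7 is read and reaches at most about 0.05 SD, under one SE, in the 10% against 5% scenario with an assumed 1 SD gap. The 10% is a power scenario, not a forecast.

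These are secondary outcomes and section 8.0 labels the regression hypothesis-generating. A reader might infer that the trial's main conclusion is at risk, but the cancer-detection comparison does not use the questionnaires. The change is worth making because it is cheap now and cannot be made after the data are collected.

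**What to change.** 1. In section 4.8.1, base the between-arm comparison on forms sent at the same fixed times from randomisation in both arms. The existing three slots a year suffice, for example every 4 months, sent regardless of where each person is in the draw-disclosure cycle.
2. Record the dates of the last draw and last disclosure with each form. Draws also recur every four months, so fixed forms may settle at one phase of the cycle; the dates let the analysis see this. Timing the forms deliberately before a disclosure is not advised, because it could replace relief with anticipatory anxiety.
3. Keep any post-disclosure form as a separate description of the experimental arm, outside the between-arm contrast.
4. Reword section 4.7 so that scheduled forms continue after a cancer diagnosis in both arms, whether or not an optional draw takes place.
5. In section 8.0, name the fixed time points to which the baseline-adjusted differences refer.

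The cost is rescheduled REDCap invitations and some extra forms for experimental and diagnosed participants. Forms are optional and take up to 20 minutes each.

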4.6 Return of Results and Follow-up Investigations

Results will be communicated to the participant by the study team member as soon as possible, and reasonable attempts will be made by the study team to return results within 2 weeks from the date of report receipt by the study team.

At the time of study enrollment, participants may be provided with an information sheet explaining a “negative” and “positive” test result (please refer to Result Information Sheet). Participants will not be routinely provided a copy of the genetic testing report. However, upon participant request, a copy of the report can be provided. A physical copy (sent by mail, or provided at the time of an in person appointment) or electronic copies (sent via email) may be provided upon request.

Return of “Negative” cfDNA assay test result

A “negative” or “cancer signal not detected” cfDNA assay results will be communicated to participants by the Study Doctor or designated member of the study team via phone. Following result disclosure, the study team member will remind the participant that the cfDNA assay result does not confirm the absence of cancer, and will reinforce the importance of continuing with standard-of-care cancer screening. If after 3 phone call attempts the study team is not able to get in contact with the participant, they will email the participant the result (please see CHARM2 Negative Result Email). A participant will only be emailed if they have already consented to email communication at the time of enrollment.

Return of “Positive” cfDNA assay test result

A “positive” or “cancer signal detected” cfDNA assay results will be communicated to participants by the Study Doctor via phone call or in-person at the time of a clinical appointment. If the Study Doctor is not able to get in contact with the participant by phone, and if they do not have an upcoming in person clinical visit, the study team may email the participant to let them know their result is now available and to arrange a time for a phone call to review the result. Following result disclosure, the Study Doctor will remind the participant that the cfDNA assay result does not confirm the presence of cancer, and that follow-up diagnostic investigations are needed. The site Study Doctor will initiate the work up for the “positive” result.

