4.12 Study Duration and Participant Time Commitments

The expected study duration for each participant will be approximately 5 years from the date of first sample collection (Table 1). We will do our best to minimize the number of on-site visits required by participants. Participants will have the option to provide research blood samples via their local community laboratory (e.g. LifeLabs or Dynacare). Result disclosure by the study team will be done over the phone, unless the participant is on-site for a clinical appointment, in which case results may be disclosed in person. Participants will be required to come into the hospital for diagnostic investigations done in follow-up to a “positive” cfDNA assay result.

Table 1. Participant requirements.

Activity	Year 1			Year 2			Year 3			Year 4			Year 5
Blood Collection ¹	x	x	x	x	x	x	x	x	x	x	x	x	
Test Results Returned to Participants (experimental cohort)	x	x	x	x	x	x	x	x	x	x	x	x	
Follow-up Diagnostic Investigations (experimental cohort)	Diagnostic investigations will ensue following a “positive” cfDNA assay result.												
Medical History and Demographic Questionnaire ²	x												
Patient-Outcome Questionnaire	x	x	x	x	x	x	x	x	x	x	x	x	
Collection of clinical data by study team.	Clinical data will be collected by the study team for up to 7 years from the date of study enrollment.												
Interviews (optional)	Interviews will be conducted over the course of the study. They will begin at the end of year 1.												

¹Tri-annual blood collection is only a study requirement for those randomized into the experimental cohort. Those in the control cohort have the option to provide up to 3 blood samples a year, ² The medical history questionnaire will be completed at least once by all participants at the time of study enrolment. Participants may be asked to update the questionnaire over the course of the study.

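### On-study questionnaires are triggered by result disclosure in the experimental arm but have no date or event in the control arm, so the arm comparison partly reflects when, and among whom, the experimental arm was measured

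*Protocol*

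**What the plan says.** The two arms share a baseline form (Section 4.8.1): "At the time of study enrollment, before randomization into the control or experimental group, participants will be provided a patient-outcome questionnaire".

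After that the rules part. Experimental participants are "asked to complete a patient-outcome questionnaire following each result disclosure by the study team (approximately 45 days following the blood collection". For the other arm, "Participants in the control group will be asked to complete the patient-outcome questionnaire up to 3 times a year". No event, date or window is attached to the control forms.

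Table 1 in Section 4.12 has one row labelled "Patient-Outcome Questionnaire", with three marks in each of Years 1 to 4. The row is not split by arm and carries no dates. Control blood draws cannot act as a matching anchor, because the footnote makes them optional: "Those in the control cohort have the option to provide up to 3 blood samples a year".

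The data feed the survey analysis in Section 8.0: baseline-adjusted mean differences between arms, with 95% confidence intervals, in distress, uncertainty, anxiety, empowerment and quality of life. The related hypothesis (Section 3.2) is that a programme of cfDNA testing improves these outcomes.

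**The concern.** Testing repeats every four months for four years. Each cycle has a period before the draw, a wait for the result, and a period after the result. Distress and uncertainty may differ between these phases. The experimental arm's on-study forms are tied to one phase only, the one after disclosure. Control forms fall at whatever times the study team chooses. A difference between arms then combines the effect of the programme with the effect of measuring one arm at a selected point in its cycle.

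There is also a selection element. An experimental form needs a draw and a disclosed result; a control form needs neither. If people who skip draws differ in anxiety or distress, they drop out of the on-study data in one arm and stay in it in the other.

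At stake is the reading of the patient-reported results. A favourable difference could be taken as the average effect of living with cfDNA surveillance when it describes how people feel after a result that is nearly always negative. A burden during the wait would go unseen.

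**Working it through.** The Protocol states no figure on this point that could be reproduced. The check sets the rules side by side and then uses the Protocol's own rates.

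**1. Rules by arm**

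| | Experimental | Control |
|---|---|---|
| Baseline | before randomisation | before randomisation |
| On-study trigger | each result disclosure | none stated |
| Frequency | up to 3 a year | at most 3 a year |
| Needs a draw and a result | yes | no |
| Date or window | about 45 days after the draw | none stated |

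**2. Share of experimental forms that follow a negative result.** Section 6.0 expects up to about 5-10% of experimental participants to be positive per year, with three results a year.
- Simple division: 5%/3 = 1.7% and 10%/3 = 3.3% positive per result.
- Compounding: 1 - 0.95^(1/3) = 1.7% and 1 - 0.90^(1/3) = 3.5%.
- So about 97-98% of result-triggered forms follow a negative result.
- This takes about one positive result per positive participant per year. If every such participant were positive at all three, the negative share would still be 90-95%.

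**3. The phase with no form.** The report target is "within 45 days of sample receipt by OICR" (Section 4.5), after which the team tries to "return results within 2 weeks from the date of report receipt by the study team" (Section 4.6). A cycle is 365.25/3 = 121.75 days. With the first target fully used, the wait is 45/121.75 = 37% of the cycle. With both fully used it is (45 + 14)/121.75 = 59/121.75 = 48%, plus transit. No on-study form is tied to this stretch.

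**4. How large a timing shift would matter (shift sizes are assumptions).** Suppose the experimental mean is displaced by s SD at the time of the form and there is no lasting programme effect. For one time point without covariate adjustment, SE = sqrt(2/n) SD; at 500 per arm this is 0.063. The probability of a two-sided p < 0.05 is 1 - Φ(1.96 - s/SE) + Φ(-1.96 - s/SE):

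| s (SD) | 500 per arm | 300 per arm |
|---|---|---|
| 0.05 | 0.12 | 0.09 |
| 0.10 | 0.35 | 0.23 |
| 0.20 | 0.89 | 0.69 |

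**5. Draw completion (assumptions).** If a share a of the experimental arm skips draws and differs by D SD, while similar controls still respond, the displacement is a × D. With a = 10-30% and D = 0.2-0.5 SD, this runs from 0.10 × 0.2 = 0.02 SD to 0.30 × 0.5 = 0.15 SD.

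**6. Withdrawal.** Section 5.3 allows withdrawal for non-compliance and stops questionnaires afterwards. Its example is missed draws in the experimental arm, so it can add to the same selection.

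**The case against.** The case on the other side is substantial.

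- **Reaction to results is part of the effect.** The Protocol Summary lists the impact of access to results as an aim, so measuring after disclosure is a legitimate choice. This stands as a reason to keep such forms. It does not make them a fair basis for an arm comparison when controls have no matching point.
- **Table 1 gives both arms the same nominal frequency.** This is true, so a reader should not infer that controls have no schedule at all. What is missing is a date or window, and the table does not override the disclosure trigger.
- **Lost forms.** One might infer that an unreachable participant or a failed sample means no form. Section 4.6 provides for emailing a negative result to those who agreed to email, and Section 4.2 allows a repeat draw. The clear route to a lost form is a missed draw.
- **Adherers against all controls.** That contrast goes too far. Questionnaires are voluntary in both arms, the control wording permits fewer than three a year, and Section 5.2 excludes people unable to comply with draws before either arm is assigned.
- **45 against 59 days.** It is tempting to call this a contradiction. The 59 days add two upper targets, while Section 4.8.1 gives an approximate value. The wording is loose, but the statements can coexist.
- **Momentary mood.** The text sets no window between disclosure and completion, so it does not show that forms capture only the immediate reaction.
- **A large spurious effect.** The documents give no size, duration or direction for a post-result shift, and no draw-completion rate. Any specific bias rests on assumption.
- **Limited stakes.** These are secondary outcomes, and Section 8.0 describes the regression as hypothesis-generating. Optional interviews also cover experience of testing.

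**Conclusion.** The point holds in a bounded form. The Protocol fixes arm-dependent timing of the on-study questionnaires and makes experimental forms depend on a completed draw and a disclosed result. Followed exactly, the plan gives arm differences that partly reflect when, and among whom, the experimental arm was measured.

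From the Protocol's own rates, about 97-98% of experimental forms would follow a negative result, taking about one positive result per positive participant per year. The size and direction of any distortion cannot be derived from the document. The shifts of 0.05-0.20 SD and the selection range of 0.02-0.15 SD are illustrations that show modest displacements could matter at this sample size.

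The comparison of cancer detection is untouched. The change should still be made in the Protocol, because a separate analysis plan can define windows but cannot recover assessments that were never scheduled at comparable times.

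**What to change.** 1. In Section 4.8.1, send the arm-comparison questionnaire to all participants in both arms at the same fixed times from randomisation, whether or not a draw or result has occurred.
2. Choose an interval that does not stay at one phase of the four-monthly draw cycle. A four-monthly form would stay locked to one phase. A five-monthly form falls at months 5, 10, 15, 20 and so on, which are 1, 2, 3 and 0 months into a four-month cycle that starts at randomisation. Up to month 45 that is nine forms, never more than three in a study year, so the present cap holds.
3. Record days since the last draw and, in the experimental arm, days since the last disclosure.
4. State in Section 8.0 that the arm comparison uses only these scheduled forms. Align Table 1.
5. Keep any post-disclosure form, after negative or positive results, as a description within the experimental arm. This preserves the aim of learning how people respond to results.
6. If forms have already been collected under the present rule, identify them and analyse them separately.

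Cost: a change to the REDCap schedule and short edits to Sections 4.8.1, 4.12 and 8.0. The fixed schedule alone means fewer forms than the 12 marks in Table 1. If post-disclosure forms are kept after every result, the experimental arm completes up to 12 in addition to the nine, each meant to take no longer than 20 minutes. The change does not recover forms from participants withdrawn under Section 5.3, so withdrawals should be reported by arm.
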